## 12 LIST OF APPENDICES

### Appendix A: Analysis Visit Windows for Safety and Efficacy Assessments

Table 12-1 Analysis Visit Windows for Safety and Efficacy Assessments			
Assessment	Visit	Target Study Day	Analysis Visit Window (in study days)
Safety Assessment			
Serum Chemistry Hematology Standard 12-lead ECG	Day 1 (Baseline)	1	≤1 Pre-dose
	Day 15	15	[1, 22]
	Week 4	29	(22, 43]
	Week 8	57	(43, 71]
	Week 12	85	(71, 99]
	Week 16	113	(99, 141]
	Week 24	169	(141, 183]
Safety Follow-up	Not applicable		Use nominal visit
Vital Signs	Day 1 (Baseline)	1	≤1
	Day 15	15	[1, 22]
	Week 4	29	(22, 43]
	Week 8	57	(43, 71]
	Week 12	85	(71, 99]
	Week 16	113	(99, 141]
	Week 24	169	(141, 183]
Safety Follow-up	Not applicable		Use nominal visit
Coagulation	Day 1 (Baseline)	1	≤1 Pre-dose
	Week 24	169	[1, 183]
	Safety Follow-up	Not applicable	Use nominal visit
Efficacy Assessment and Pharmacodynamic Assessment			
Spirometry	Day 1 (Baseline)	1	≤1 Pre-dose
	Day 15	15	(1, 22]
	Week 4	29	(22, 43]
	Week 8	57	(43, 71]
	Week 12	85	(71, 99]
	Week 16	113	(99, 141]
	Week 24	169	(141, 183]
Safety Follow-up	Not applicable		>183
Sweat Chloride	Day 1 (Baseline)	1	≤1 Pre-dose
	Week 4	29	(1, 43]
	Week 8	57	(43, 71]
	Week 12	85	(71, 127]
	Week 24	169	(127, 183]
CFQ-R	Day 1 (Baseline)	1	≤1
	Week 4	29	(1, 43]
	Week 8	57	(43, 71]
	Week 12	85	(71, 99]
	Week 16	113	(99, 141]
	Week 24	169	(141, 183]
	Safety Follow-up	Not applicable	

**Table 12-1 Analysis Visit Windows for Safety and Efficacy Assessments**

Assessment	Visit 	Target Study Day	Analysis Visit Window (in study days) 
Weight, Height and BMI (and the corresponding z-score)	Day 1 (Baseline)	1	≤1
	Day 15	15	(1, 22]
	Week 4	29	(22, 43]
	Week 8	57	(43, 71]
	Week 12	85	(71, 99]
	Week 16	113	(99, 141]
	Week 24	169	(141, 183]
	Safety Follow-up	Not applicable	>183

Notes:

 Visit name for analysis purpose is used to report data in tables and figures.

 The analysis visit windows will be applied using the following rules for both scheduled and unscheduled visits:

- If no numerical measurement is available within a visit window, the measurement will be considered missing for the visit.
- If there is more than 1 numerical measurement available within a visit window, use the following rules:
  - The measurement closest to the target day will be used; or
  - If there are multiple measurements with the same distance from the target day, the latest measurement will be used.

 For lab, ECG and vital sign measurement collected on the date of first dose of study drug, if it cannot be determined whether the measurement is before or after the first dose:

- Scheduled measurement will be treated as pre-dose observation.
- Unscheduled measurement will be treated as post-dose observation.

Derived Variables:

- Age (in years) at first dose date and nominal visit (for demographics, listing and the calculation of [percent] predicted spirometry variables):
 

Obtain the age at informed consent (in days) in “yy, mm” format (e.g., 24 years, 6 months) from the Vital Signs (VS) page at the Screening Visit, and add 0.5 month to convert to days.

Obtain the informed consent date.

Then age (in years) at first dose or nominal visit = [(first dose date or nominal visit date – informed consent date) in days + age at informed consent (in days)]/365.25.
- Age (in months) at nominal visit (for use in calculation of BMI and weight z-score):
 

Obtain the age at informed consent (in months) in “yy, mm” format (e.g., 24 years, 6 months) from Vital Signs (VS) page at the Screening Visit.

Obtain the informed consent date.

Then age (in months) at nominal visit = integer part of {(age at informed consent (in months) + 0.5 + diff(first dose date or post-baseline visit date, informed consent date) in months)} + 0.5.
- Missing first dose date or last dose date
 

If the first dose date is missing, use Day 1 visit date to impute.

If the last dose date is missing or partial date is reported, the last dose date will be imputed based on, in descending order priority, the Early Treatment Termination (ETT) visit date, last visit date before the Safety

Table 12-1 Analysis Visit Windows for Safety and Efficacy Assessments			
Assessment	Visit	Target Study Day	Analysis Visit Window (in study days)
			
Follow-up, or the last study drug administration date from EX SDTM domain, as appropriate. The imputation algorithm will ensure the imputed last dose date does not exceed the study participation end date.
 
4. Sweat Chloride:            Non-missing sweat chloride concentrations from the left arm and right arm with assessment end date/time for a given arm up to 30 minutes after first dose time in treatment period will be considered for baseline.
 
5. Electrocardiogram:            Baseline is defined as the most recent pretreatment measurement before the first dose of study drug in the Treatment Period. If multiple ECG measurements are obtained on the same calendar day during the TE period,
 
 
○ For summary purpose, the calculated average ECG will be used as the ECG value on that day;
 
○ For threshold analysis purpose, all reported ECG values will be used.
 

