### **9.1.4 Early Termination of Treatment**

If a subject prematurely discontinues study drug treatment, an Early Termination of Treatment (ETT) Visit should be scheduled as soon as possible after the decision to discontinue treatment. Subjects who prematurely discontinue treatment will also be required to complete the Safety Follow-up Visit, approximately 28 days after their last dose of study drug. The assessments performed at the Safety Follow-up Visit are listed in [Table 3-2](#).

If the ETT Visit occurs 3 weeks or later following the last dose of study drug, then the ETT Visit will replace the Safety Follow-up Visit, and a separate Safety Follow-up Visit will not be required.

Subjects who prematurely discontinue study drug treatment will continue to complete all scheduled study visits for assessments following completion of the ETT Visit, as detailed in [Table 3-2](#). Data regarding concomitant antibiotic therapy for sinopulmonary signs/symptoms will also continue to be collected for these subjects.

If a subject withdraws from the study and also withdraws consent or assent, no further assessments will be performed. Vertex may retain and continue to use any data and samples collected before such withdrawal of consent or assent.

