### **9.2.5 Study Drug Exposure**

Duration of study drug exposure (in days) will be calculated as: last dose date of study drug – first dose date of study drug + 1, regardless of study drug interruption, and will be summarized descriptively.

Study drug exposure (in weeks) will be summarized descriptively by the number of subjects (n), mean, SD, median, min, and max. It will also be summarized in categories for Treatment Period:  $\leq 1$  week,  $>1-\leq 2$  weeks,  $>2-\leq 4$  weeks,  $>4-\leq 8$  weeks,  $>8-\leq 12$  weeks,  $>12-\leq 16$  weeks,  $>16-\leq 20$  weeks,  $>20-\leq 24$  weeks, and  $>24$  weeks, using counts and percentages. Additionally, the total study drug exposure, defined as the sum total of the study drug exposure across all subjects (in patient-weeks and patient-years), will be provided.

Exposure summaries will be based on the Safety Set, and presented by treatment group and overall.

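### A partial last-dose date is replaced by the ETT visit date with no limit to the reported month, which can overstate exposure and lengthen the treatment-emergent period

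*SAP*

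**What the plan says.** The rule is in SAP Appendix A, under the derived variables that follow Table 12-1. Its trigger covers both cases: "If the last dose date is missing or partial date is reported, the last dose date will be imputed based on, in descending order priority". Three sources follow. The list begins with "the Early Treatment Termination (ETT) visit date, last visit date before the Safety" (the sentence runs on across a page break) and ends with "Follow-up, or the last study drug administration date from EX SDTM domain, as appropriate". So a visit date ranks above a recorded administration. One limit is written: "The imputation algorithm will ensure the imputed last dose date does not exceed the study participation end date". Nothing ties the imputed date to a month or year that was reported.

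Protocol section 9.1.4 says of the ETT visit that the "Visit should be scheduled as soon as possible after the decision to discontinue treatment". The same section also provides for a late one: "If the ETT Visit occurs 3 weeks or later following the last dose of study drug", it takes the place of the Safety Follow-up Visit. No upper limit on the delay is given.

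The last-dose date then feeds:
- SAP 9.2.5: "Duration of study drug exposure (in days) will be calculated as: last dose date of study drug" minus first dose date plus 1, and total patient-weeks and patient-years.
- SAP 9.2.6: exposure duration is in the denominator of both compliance measures.
- SAP 9.1: the TE period ends 28 days after the last dose or at completion of participation, whichever is first.

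For other partial dates the SAP keeps what was reported. Appendix B takes the last day of the month or year for a medication stop date. Appendix E takes the earlier of month end and end of participation for an adverse event (AE) end date.

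**The concern.** A site that reports the month of the last dose but not the day has given usable information, and the rule as written does not use it. When the ETT visit falls in a later month, the imputed last dose contradicts the record.

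Exposure is then too long. The tablets-taken percentage falls, because its denominator grows while the tablet count does not. The interruption-based compliance figure can only stay the same or rise. A longer TE period turns post-treatment AEs into treatment-emergent ones. Under SAP 9.4.1 the summary tables cover treatment-emergent AEs only, and post-treatment AEs appear only in listings, so the shift moves events into the tables. Laboratory, ECG and vital-sign summaries and the concomitant-medication class depend on the same period.

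**Working it through.** The documents give no figure for this point, so there is none to reproduce. The check is date arithmetic on the stated rules.

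**Inputs from the documents.** Exposure = last dose − first dose + 1 (SAP 9.2.5). TE end = the earlier of last dose + 28 days and completion of participation (SAP 9.1). Week 24 is Day 169 (SAP Table 12-1).

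**Assumptions.** First dose on Day 1; participation to Day 169; L is the lag in days from true last dose to ETT visit. L is not given in the documents, so it is varied. For the calendar columns, all 365 last-dose dates of one year count equally.

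**Worked case, true last dose Day 60, L = 21.**
- Imputed last dose: 60 + 21 = Day 81.
- Exposure: 81 instead of 60 days; 21/60 = 35% too long.
- TE end: 81 + 28 = Day 109 instead of 60 + 28 = Day 88. Both are before Day 169, so the cap does not act. AEs starting on Days 89 to 109 become treatment-emergent.
- Tablets taken, fully adherent subject: 100 × 60/81 = 74.1% instead of 100%.

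**Range over L, true last dose Day 60.** The last two columns do not depend on the Day 60 assumption. The month limit is the earlier of the last day of the reported month and the ETT date.

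| L (days) | Exposure (days) | TE end | Tablets taken | Share of last-dose dates whose ETT date leaves the month | Mean overstatement with month limit (days) |
|---|---|---|---|---|---|
| 7 | 67 (+12%) | Day 95 | 89.6% | 23% | 6.1 |
| 14 | 74 (+23%) | Day 102 | 81.1% | 46% | 10.5 |
| 21 | 81 (+35%) | Day 109 | 74.1% | 69% | 13.4 |
| 28 | 88 (+47%) | Day 116 | 68.2% | 92% | 14.7 |
| 35 | 95 (+58%) | Day 123 | 63.2% | 100% | 14.7 (maximum 30) |

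At L = 21 the exposure error is 70% for a true last dose on Day 30 (21/30) and 21% for Day 100 (21/100).

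**Does the participation-end limit help?** For a subject who stops drug early and keeps consent, participation ends at the latest of the Week 24, ETT and Safety Follow-up visits. That is never before the ETT date, so the limit cannot pull back an imputed ETT date. It can shorten the TE period. Take a true last dose on Day 150, Week 24 on Day 169 and ETT on Day 171. The lag is 21 days, so the ETT visit replaces Safety Follow-up and participation ends on Day 171. TE end is Day 171 with either last-dose date (150 + 28 = 178 and 171 + 28 = 199 both exceed 171). Exposure is still 21 days too long.

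**The case against.** **The late visit is a contingency.** The protocol wants the ETT visit promptly. At a 7-day lag the date leaves the reported month for 23% of last-dose dates, and a month limit lowers the mean error only from 7 to 6.1 days. This stands: the gain comes from late visits, and their number is not known.

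**The wording leaves discretion.** The rule bases the date on the listed sources and ends with a qualifier about appropriateness. A programmer could respect the reported month, but nothing requires it.

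**The direction is conservative.** A longer TE period counts more events, the rule is the same in both arms, safety is descriptive only, and the SAP already classes AEs of unclear timing as treatment-emergent. That is fair for event counts. It does not answer the inflated patient-time or the distorted tablets-taken figure. Appendices B and E concern other variables, so this is a difference in convention and not a contradiction.

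**Stronger readings that the documents do not support.**
- A reader might infer that, once the ETT visit is 3 weeks late, the TE period always runs at least 21 + 28 = 49 days past the true last dose. That is the uncapped value; in the Day 150 case above the period runs 21 days past it.
- A reader might infer that partial dates cluster in early stoppers. An ETT visit arises only after early discontinuation, but nothing shows that partial dates are commoner there. Drug counts at clinic visits and data queries work against them.
- A reader might want recorded administrations (EX) ranked first for fully missing dates too. The documents do not say what EX holds. Protocol 9.6.1 requires dose times around pharmacokinetic samples, and Table 3-2 schedules these up to Week 16 and at ETT, with none at Week 24. If the last record were at Week 16 (an assumption), a completer would lose about 24 − 16 = 8 weeks of exposure. The present rule, using the Week 24 visit, errs by about 1 day, since the final dose is due the evening before.

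**Conclusion.** The point holds for partial dates. As written, the rule can place the last dose after the reported month. It overstates exposure and the compliance denominators by the ETT lag, and can extend the TE period by up to that lag, subject to the cap at completion of participation. In the Day 60 case the error is 21 days on exposure and on TE end.

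This needs a partial last-dose date and a delayed ETT visit in the same subject. The reported month is overridden only if the visit falls in a later month. The number affected is unknown and probably small. The primary and key secondary tests do not use this date: they rest on visit-windowed data, and the exacerbation analysis period ends at the last efficacy assessment, not the last dose. It is a minor but easily corrected matter of safety, exposure and compliance reporting.

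**What to change.** Amend the last-dose entry in SAP Appendix A for partial dates only. When the month and/or year is reported, impute the earliest of (a) the last day of that reported period, (b) the ETT visit date, or the last visit before Safety Follow-up if there was no ETT visit, and (c) the study participation end date. The result must never be earlier than the last documented dose. Keep the existing visit-first order for fully missing dates.

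The cost is one sentence in the SAP and a few lines of derivation code. Some error remains: up to about 30 days when only the day is missing (a last dose on the first of a 31-day month with a late ETT visit). When only the year is known, the limit will often not act. At short lags the change makes little difference and does no harm.

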## Appendix B: Imputation Rules for Missing Prior/Concomitant Medication Dates

Imputation rules for missing or partial medication start/stop dates are defined below:

1. Missing or partial medication start date:
  - a. If only DAY is missing, use the first day of the month.
  - b. If DAY and Month are both missing, use the first day of the year.
  - c. If DAY, Month and Year are all missing, use a date before the first dose date (in practical, use Jan. 01, 2000 to impute).
2. Missing or partial medication stop date:
  - a. If only DAY is missing, use the last day of the month.
  - b. If DAY and Month are both missing, use the last day of the year.
  - c. If DAY, Month and year are all missing, assign ‘continuing’ status to stop date (in practical, use Dec. 31, 2050 to impute).

In summary, the prior, concomitant, or post categorization of a medication is described below.

**Table 12-2 Prior, Concomitant, and Post Categorization of a Medication**

Medication Start Date	Medication Stop Date		
	< First Dose Date of Study Drug	≥ First Dose Date and ≤ End Date of TE Period	> End Date of TE Period
< First dose date of study drug	P	PC	PCA
≥ First dose date and ≤ End date of TE period	-	C	CA
> End date of TE period	-	-	A

P: Prior; C: Concomitant; A: Post

Imputation rules for missing and/or partial dates of non-pharmacological treatment/procedure will follow the same imputation rule.

## Appendix C: Details of GLI Equations for Calculating ppFEV1

Percent predicted values will be calculated for parameters of FEV1, [REDACTED] using the Quanjer GLI-2012 Regression Equations and Lookup Tables.

The regression equations and lookup tables required to implement the Quanjer GLI-2012 predicted values are available in:

Philip H. Quanjer, Sanja Stanojevic, Tim J. Cole, Janet Stocks. Quanjer GLI-2012 Regression Equation and Lookup Tables (Version 7 April 2013). Global Lung Function Initiative. [online] Available at: <http://www.ers-education.org/home/browse-all-content.aspx?idParent=138978> [Accessed Mar 26, 2018].

The instructions and tools on how to implement the Quanjer GLI-2012 equations are:

Philip H. Quanjer, Sanja Stanojevic, Tim J. Cole, Janet Stocks. Implementing GLI-2012 regression equations (Version 19 July 2015). Global Lung Function Initiative. [online] Available at: <http://www.ers-education.org/home/browse-all-content.aspx?idParent=138979> [Accessed Mar 26, 2018].

Sanja Stanojevic. GLI-2012 - SAS Macro (Version 2, 7 April 2013). Global Lung Function Initiative. [online] Available at: <http://www.ers-education.org/home/browse-all-content.aspx?idParent=138988> [Accessed Mar 26, 2018].

Data handling rule for spirometry is as follows:

- Input age and height with at least 2 decimal place
- Use height at screening regardless if height is collected at other study visits for subjects whose age at informed consent is >21 years. For subjects with age <=21 years, height collected at the respective visit should be used; if the height at the respective visit is not available, the last non-missing record will be used.
- For race, map the CRF reported Black or African American to Black, all other races in CRF (except White) are mapped to 'other'; multiple checks for race in CRF are also mapped to 'other'; white is a reference race in the equations and assumes 0 values for all race coefficients in the GLI equations.

## Appendix E: Imputation Rules for Missing AE dates

Imputation rules for missing or partial AE start date are defined below. If the imputed AE start date is before the study informed consent date, the AE start date will be imputed using the study informed consent date.

- **If only Day of AE start date is missing:**

- If the full (or partial) AE end date is NOT before the first dose date of the Treatment Period or AE end date is missing, then
  - if AE start year and month are equal to the month and year of first dose date of the Treatment Period, then impute the AE start day as the day of first dose date of the Treatment Period;
  - else impute the AE start day as 1.
- else impute the AE start day as 1.

Compare the imputed AE start date with TE period to determine whether the AE is pretreatment AE, TEAE or post-treatment AE.

- **If Day and Month of AE start date are missing:**

- If the full (or partial) AE end date is NOT before the first dose date of the Treatment Period or AE end date is missing, then
  - if AE start year is equal to the year of first dose date of the Treatment Period, then impute the AE start month and day as the month and day of first dose date of the Treatment Period;
  - else impute the AE start month as January and day as 1.
- else impute the AE start month as January and day as 1.

Compare the imputed AE start date with TE period to determine whether the AE is pretreatment AE, TEAE or post-treatment AE.

- **If Year of AE start date is missing:**

If the year of AE start is missing or AE start date is completely missing then query site and

- If the full (or partial) AE end date is NOT before the first dose date of the Treatment Period or AE end date is missing, then impute the AE start date as the first dose date of the Treatment Period;
- else impute the AE start date as the informed consent date.

Imputation rules for partial AE end date are defined below:

- Impute the AE end date as min (the last day of the month, end of study participation) if day is missing, or min (Dec, end of study participation) if month is missing.
  - For the IA purpose, if the end of study date is missing, then the IA data cutoff date will be used instead in the imputation

## Appendix F: Criteria for Threshold Analysis

**Table 12-3 Threshold Analysis Criteria for Laboratory Tests (as applicable)**

Parameter	Threshold Analysis	Comments
Clinical Chemistry (LFT)		
ALT	>ULN - ≤3xULN >3x - ≤5xULN >5x - ≤8xULN >8x - ≤20.0xULN >20.0xULN	FDA DILI Guidance Jul 2009.
AST	>ULN - ≤3xULN >3x - ≤5xULN >5x - ≤8xULN >8x - ≤20.0xULN >20.0xULN	FDA DILI Guidance Jul 2009.
ALT or AST	(ALT>ULN - ≤ 3xULN) or (AST>ULN - ≤3xULN) (ALT>3x - ≤5xULN) or (AST>3x - ≤5xULN) (ALT>5x - ≤8xULN) or (AST>5x - ≤8xULN) (ALT>8x - ≤20xULN) or (AST>8x - ≤20xULN) ALT>20xULN or AST>20xULN	FDA DILI Guidance
Alkaline Phosphatase	>ULN - ≤1.5xULN >1.5 - ≤2.5xULN >2.5 - ≤5.0xULN >5.0 - ≤20.0xULN >20.0xULN	FDA DILI Guidance Jul 2009.
Total Bilirubin	>ULN - ≤1.5xULN >1.5 - ≤2xULN >2 - ≤3xULN >3 - ≤10xULN >10xULN	FDA DILI Guidance Jul 2009.
Direct Bilirubin	>ULN - ≤1.5xULN >1.5 - ≤2xULN >2 - ≤3xULN >3 - ≤10xULN >10xULN	FDA DILI Guidance Jul 2009.
ALT and Total Bilirubin	ALT>3xULN and TBILI>2xULN	FDA DILI Guidance Jul 2009.
AST and Total Bilirubin	AST>3xULN and TBILI>2xULN	FDA DILI Guidance Jul 2009.
(ALT or AST) and Total Bilirubin	(ALT>3xULN or AST>3xULN) and TBILI>2xULN	FDA DILI Guidance Jul 2009.

**Table 12-3 Threshold Analysis Criteria for Laboratory Tests (as applicable)**

Parameter	Threshold Analysis	Comments
GGT	>ULN - ≤2.5xULN >2.5 - ≤5.0xULN >5.0 - ≤20.0xULN >20.0xULN	CTCAE grade 1-4
Clinical Chemistry (NON-LFT)		
Albumin	<LLN - ≥30 g/L <30 - ≥20 g/L <20 g/L	CTCAE grade 1-3
Amylase	>1x - ≤1.5xULN >1.5x - ≤2xULN >2x - ≤5xULN >5xULN	Criteria based upon CTCAE
Creatinine	>ULN - ≤1.5xULN >1.5 - ≤3.0xULN >3.0 - ≤6.0xULN >6.0xULN	CTCAE grades 1-4
Lipase	>ULN - ≤1.5xULN >1.5x - ≤2xULN >2x - ≤5xULN >5xULN	Criteria based upon CTCAE
Total protein	<LLN >ULN	No CTCAE
Creatine kinase	>ULN - ≤2.5xULN >2.5 - ≤5xULN >5 - ≤10xULN >10xULN	CTCAE grades 1-4
Hematology		
Hemoglobin	Hgb decreased (anemia) <LLN - ≥100 g/L <100 - ≥80 g/L <80 g/L	CTCAE grade 1-3
	Hgb increased >ULN - ≤20 g/L above ULN >20 g/L above ULN - ≤40 g/L above ULN >40 g/L above ULN	CTCAE grade 1-3
Platelets	Platelet decreased <LLN - ≥75.0 x 10e9 /L <75.0 - ≥50.0 x 10e9 /L <50.0 - ≥25.0 x 10e9 /L <25.0 x 10e9 /L	CTCAE grade 1-4
	Platelet increased >ULN	No CTCAE available
Reticulocytes/Erythrocytes (%)	<LLN >ULN	No CTCAE

